9.8.2 Data and Safety Monitoring Board

Because this is a small study with only 21 subjects, no DSMB will be used for this study. Data and safety monitoring will be conducted by an individual (Study Monitor) who is not an investigator on this study (see above).

10 Data Handling and Record Keeping

10.1 Confidentiality

Information about study subjects will be kept confidential and managed according to the requirements of the Health Insurance Portability and Accountability Act of 1996 (HIPAA). Consistent with these regulations a signed authorization will be obtained that informs each subject of the following:

- What protected health information (PHI) will be collected from subjects in this study
- Who will have access to that information and why
- Who will use or disclose that information
- The rights of a research subject to revoke their authorization for use of their PHI.

In the event that a subject revokes authorization to collect or use PHI, the investigator, by regulation, retains the ability to use all information collected prior to the revocation of subject authorization. For subjects that have revoked authorization to collect or use PHI, attempts should be made to obtain permission to collect at least vital status (i.e. that the subject is alive) at the end of their scheduled study period.

10.2 Source Documents

Source data are all information, original records of clinical findings, observations, or other activities in a clinical trial necessary for the reconstruction and evaluation of the trial. Source data are contained in source documents. Examples of these original documents, and data records include: hospital records, clinical and office charts, laboratory notes, memoranda, subjects' diaries or evaluation checklists, pharmacy dispensing records, recorded data from automated instruments, copies or transcriptions certified after verification as being accurate and complete, microfiches, photographic negatives, microfilm or magnetic media, x-rays, subject files, and records kept at the pharmacy, at the laboratories, and at medical-technical departments involved in the clinical trial.

10.3 Case Report Forms

The study case report form (CRF) is the primary data collection instrument for the study. All data requested on the CRF must be recorded. All missing data must be explained. If a space on the CRF is left blank because the procedure was not done or the question was not asked, write "N/D". If the item is not applicable to the individual case, write "N/A". All entries should be printed legibly in black ink. If any entry error has been made, to correct such an error, draw a single straight line through the incorrect entry and enter the correct data above it. All such changes must be initialed and dated. DO NOT ERASE OR WHITE OUT ERRORS. For clarification of illegible or uncertain entries, print the clarification above the item, then initial and date it.

Copies of completed CRFs with subject IDs will be scanned and sent to the lead study coordinator at UNC for verification through the study database. Data should be entered in the study database within 5 business days to ensure timely entry.

The coordinator at each site will complete the first CRF together with one of the Co-PIs to verify that it is completed correctly. Then, we will verify a randomly selected 25% of all source docs at the conclusion of data collection. Randomization will occur on a visit level and not per patient. The randomization for this verification will be generated using a random number generator in Excel. A concealed randomization look-up table will be generated in collaboration with the biostatistician and installed in the REDCap database. Assignments remain concealed to the staff until the moment the participant is enrolled online in the REDCap database.

10.4 Record Retention

It is the investigators' responsibility to retain study essential documents during the investigation and for a period of 2 years after the latter of the following two dates: The date on which the investigation is terminated or completed, or the date that the records are no longer required for purposes of supporting a premarket approval application or a notice of completion of a product development protocol. These documents should be retained for a longer period if required by an agreement with the sponsor. In such an instance, it is the responsibility of the sponsor to inform the investigator/institution as to when these documents no longer need to be retained. Research records and original signed consent forms are to be retained by principal investigator for at least 6 years if the form includes authorization for use of private health information. Investigators may need to retain these documents for a longer period if required by an agreement with a sponsor or per other applicable regulatory requirements. The 6 year minimum retention of authorizations complies with the privacy regulation requirements.

10.5 IRB Documentation

The co-principal investigators and research coordinator will be responsible for maintaining IRB correspondence. IRB approved forms maintained, as part of the study will include the subject consent form and the HIPAA authorization form.

11 Study Monitoring, Auditing and Inspecting

11.1 Study Monitoring Plan

11.1.1 Locations

Initial enrollment will occur at either an orthopedic clinic or in an interventional radiology clinic in the Northern Virginia area or at UNC-Chapel Hill. The procedures will be performed in Vascular Institute of Virginia Interventional Radiology or UNC-Chapel Hill procedural suites. Follow-up visits will occur at Vascular Institute of Virginia, UNC-Chapel Hill, or via phone or teleconference.

11.1.2 Study Staff Responsibilities and Training

CITI Training:

The investigators and all staff involved in the study will have completed their required CITI training in the protection of human research subjects and Good Clinical Practice training. Alternate training modules, as requested by local IRB, may also suffice.

Drs. [name], [name], and [name] (fellowship trained interventional radiologists with subspecialty board certification) will be the only primary operators for each of the GAE's. Drs. [name], [name], and [name] have performed more than 600 arterial embolization procedures.

Any of the investigators may conduct follow-up visits as determined by the subjects' and investigators' availability.

All subjects will be coded by an alphanumeric identifier (letters [initials] and site number) and subject identity will be kept confidential. Subjects will be apprised during the informed consent review that they have the right to voluntarily withdraw from the study at any time for any reason, and that his decision will not affect his medical care, but for attrition analysis subjects will be asked their reason for withdrawal.

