3.1 General Design

This will be a single-blinded randomized-controlled study of GAE versus placebo in a small population with knee pain secondary to arthritis to determine safety and efficacy. After IRB approval of a written informed consent and over, approximately a 24 month duration, N=21 subjects will be recruited. Only subjects ≥ 40 years will be screened for study recruitment. Subjects will be randomized in a 2:1 ratio of GAE:Placebo and will be blinded from study treatment (see flow chart below). The placebo procedure will be a diagnostic angiogram of the knee, without embolization. Appropriate measures will be taken to ensure patients and nursing staff caring for the patient are blinded to assignment. Each patient will be told at the time of recruitment that they may be randomly assigned to sham, but if after 1 month they have not had symptom improvement, their assigned procedure would be revealed and, if they had undergone a sham procedure, they will be allowed to proceed with embolization. This second procedure should be shorter than a complete angiogram and embolization, as the detailed angiogram will not need to be repeated, and therefore both arms will have similar total radiation dose.

Clinical procedures and evaluations will consist of a preoperative screening assessment to determine if the potential study subject meets the inclusion and exclusion criteria, enrollment, surgical procedure for geniculate artery embolization, and follow-up visits at 24 hours, 2 weeks, 1, 3, 6, & 12 months. An MRI will be performed after the 1-month visit in those patients who underwent embolization to detect a change in synovial vascularity and to exclude complication.

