5.5 Blinding of Study

Following randomization, efforts will be made to blind the subject to the study procedure. Patients will not be informed to their treatment or placebo arm. As the procedures of a diagnostic angiogram and embolization are similar (femoral artery access, angiogram, post-operative care), the subject will inherently not know if he/she received the treatment or placebo. The post-operative staff caring for the patient will not be informed as to the treatment the patient received. Datasets for each arm will be presented for analysis by statistician labeled as treatment arm (i.e. A, B or C).

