6.6 Visit 6a and 6b - 3 Month Follow-Up for blinded subjects

Subjects will be seen in clinic or contacted by phone or by teleconference, per the subject's preference, 90 +/- 10 days following GAE or sham procedure. The WOMAC questionnaire and VAS pain score will be completed and subjects will be evaluated for possible adverse events. Subjects will also provide an update about the necessity/frequency of pre-established conservative therapies. If an AE is suspected based on change in pain scores or functionality, an appropriate

work-up will be performed which may include MRI.

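### Operators who know the allocation are not excluded from follow-up visits, and the plan names no blinded person, or self-completion, for the two self-reported primary outcomes

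*Combined protocol and SAP*

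**What the plan says.** Section 11.1.2 restricts who performs the procedure: three interventional radiologists "will be the only primary operators for each of the GAE's". It then opens follow-up to everyone: "Any of the investigators may conduct follow-up visits", depending only on when subject and investigator are available.

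Section 3.1 declares the blinding level: "This will be a single-blinded randomized-controlled study of GAE versus placebo". It adds: "Appropriate measures will be taken to ensure patients and nursing staff caring for the patient are blinded to assignment". Section 5.5 covers the ward: "The post-operative staff caring for the patient will not be informed as to the treatment the patient received". It also has the datasets passed to the statistician under arm labels. Neither section mentions the person who collects outcomes at follow-up.

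Sections 6.5, 6.6, 6.8 and 6.14 let the subject choose a clinic, phone or teleconference contact at 1, 3, 6 and 12 months. Each uses the same passive sentence for the instruments: "The WOMAC questionnaire and VAS pain score will be completed". None says by whom, or whether the subject fills them in alone.

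**The concern.** Both primary endpoints (3.2) are the subject's own account of pain and function, and the trial exists to separate embolization from placebo response (1.2). Subject blinding is therefore its main protection. A follow-up contact with someone who knows the allocation can weaken it in two ways: through the wording, prompting or tone with which items are put to the subject, and through cues that let the subject guess the arm. Phone contacts are the most exposed, because someone may have to read out the items and record the answers.

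The same contacts yield other data open to the same influence. At 1 month, sham subjects who do not report improvement are unblinded and offered embolization (6.5). Throughout follow-up, coordinators and physicians ask about new or escalated therapy (5.3), which counts as treatment failure once the 14-day post-operative period is over (5.4). Bias that enters at collection cannot be removed in the analysis.

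**Working it through.** **Who knows, who is blinded, who collects**

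| Role | Knows the allocation? | May run follow-up? |
|---|---|---|
| Operators | Yes, necessarily | Yes; 11.1.2 does not exclude them |
| Other investigators | Not stated | Yes (11.1.2) |
| Coordinators | Not stated; REDCap conceals assignment from staff only until online enrolment (10.3) | Not assigned; they ask about therapy changes (5.3) |
| Nursing and post-operative staff | Blinded (3.1, 5.5) | Not assigned |
| Collector of WOMAC and VAS | Not specified | Not specified |

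So following the plan as written can put an operator on the phone with a subject whom he or she treated, at the visit where the primary outcomes are recorded.

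**Reproducing the plan's figures**

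Inputs: 21 subjects at 2:1, so 14 and 7 (3.1); one-sided test (8.1) at 0.05 (8.2); WOMAC mean 12.2 and SD 1.9, VAS mean 72 and SD 13.3 (8.1). Two-sample t-test, df = 19, critical t = 1.729, noncentrality = d × √(14×7/21) = 2.160d.

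- WOMAC: 0.16 × 12.2 = 1.952; d = 1.952/1.9 = 1.027; power 68.9% (plan: 69.1%).
- VAS: 0.15 × 72 = 10.8 mm; d = 10.8/13.3 = 0.812; power 51.9% (plan: 51.7%).

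**Illustration of a collection bias**

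Assume no true effect and a pure shift b in favour of GAE. The chance of p<0.05 is the power formula with d = b/SD. The 3-5 mm shift is an assumption, equal to 28-46% of 10.8 mm (3/10.8 and 5/10.8). The SD of 20 is also an assumption.

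Section 8.2 reads the p-value together with the clinically relevant difference. The last column therefore also requires an observed difference above 10.8 mm. It is obtained by integrating the normal probability for the difference over the chi-squared distribution (19 df) of the pooled variance.

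| SD | Shift | d | p<0.05 | p<0.05 and difference >10.8 mm |
|---|---|---|---|---|
| 13.3 | 0 | 0 | 5.0% | 3.4% |
| 13.3 | 3 mm | 0.226 | 12.0% | 9.0% |
| 13.3 | 5 mm | 0.376 | 19.4% | 15.4% |
| 20 | 0 | 0 | 5.0% | 5.0% |
| 20 | 3 mm | 0.150 | 9.1% | 9.1% |
| 20 | 5 mm | 0.250 | 13.1% | 13.0% |

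The standard error is SD × √(1/14 + 1/7), which is 6.16 mm at SD 13.3 and 9.26 mm at SD 20. At SD 13.3 the smallest significant difference is on average about 1.729 × 6.16 = 10.65 mm, close to 10.8, so the second criterion removes some false positives. At SD 20 it is about 1.729 × 9.26 = 16.0 mm, and the second criterion hardly matters.

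For WOMAC, a shift of a quarter of the relevant difference (0.49 points) gives p<0.05 in 13.4% of trials. The 16% criterion protects more here. The standard error is 1.9 × 0.463 = 0.88, so the chance of exceeding 1.952 is at most P(Z > (1.952 − 0.49)/0.88) ≈ 5%, against at most P(Z > 1.952/0.88) ≈ 1.3% with no shift.

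**The case against.** The strongest reply is that the trial is openly single-blind, that both instruments are patient-reported, and that the subjects are blinded. No assessor rates anything, so any influence is indirect. That stands as a limit on the concern. It does not remove it, because the plan never states that subjects complete the instruments alone. Operators cannot be blinded, but outcome collection can be kept apart from them.

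Four stronger readings are tempting, and the documents do not support them.

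- A reader might infer that operators take WOMAC and VAS themselves. The visit sections say only that the instruments get completed, which is compatible with self-completion. Section 6.1 speaks of administering WOMAC, but at screening, before randomization.
- A reader might infer that an operator decides whether a sham subject has failed to improve. Section 6.5 makes this depend on what the subject reports, and no section gives the judgement to an operator. At most, an interviewer could influence the report.
- A reader might take 12-19% as the trial's false-positive rate. It is the p-value alone under an assumed shift, in a single-time-point t-test and not the planned random coefficient model.
- A reader might conclude that handing follow-up to the coordinator settles the matter at no cost. Staff may see the assignment in REDCap after enrolment (10.3), and device lot numbers go into the procedure CRF (5.6.4). The 1-month MRI is for GAE subjects only (6.5), and AE assessments must be made by an investigator (11.1.4). A coordinator would be blind only if access and tasks were separated.

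**Conclusion.** The concern holds as a gap in the plan. Outcome collection is neither assigned nor blinded, and the operators are not excluded from the visits where both primary endpoints are recorded. The plan permits this; it does not require it, and nothing shows that bias will occur. Its size and direction are unknown.

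The illustration shows only that a trial of 14 against 7, tested one-sided at 5%, has little margin. An assumed VAS shift of less than half the relevant difference would roughly double to quadruple the 5% rate on the p-value at SD 13.3. The rate would be 9-15% under the joint criterion at that SD, and 9-13% at SD 20 under either rule. These figures rest on the assumed shift, the assumed SD of 20, the t-test simplification and no dropout.

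The change is worth making because it is cheap and protects both primary endpoints. Sample size, alpha and stated power are unaffected.

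**What to change.** 1. In 5.5 and the visit sections, state that subjects complete WOMAC and VAS themselves, on paper or through a REDCap survey link, before any contact with an investigator. At 1 month, state that this comes before the MRI and before any unblinding.
2. Where a contact is needed to collect the scores, state that it is made by a coordinator or non-operating investigator without access to the allocation. Restrict access to the REDCap assignment and to the procedure CRF, which carries the lot number, accordingly.
3. Reword 11.1.2 to match. AE assessment stays with an investigator, as 11.1.4 requires, and takes place after the scores are recorded.

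Self-completion before contact is the core of the change. It largely avoids the access problems and should need no extra staff; that last point is a judgement from the coordinators and database described in 10.3, not a statement in the documents.

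The cost is protocol wording, a survey link, some separation of REDCap and CRF access, and less flexibility in scheduling investigators. The GAE-only MRI at 1 month remains a separate route to unblinding at later visits, which this change does not close.

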11.1.3 Quality Assurance and Quality Control

The research coordinator will monitor the study files on a monthly basis to ensure the appropriate regulatory and IRB documentations are on file and up to date. The research coordinator will also be responsible for ensuring proper study documentation in order to verify compliance with Institutional policy, IRB, FDA and GCP guidelines in the following areas: Informed consent, Protocol, Source Documents and Electronic Case Report Forms.

11.1.4 Safety Monitoring

The research coordinator will complete the appropriate report form and logs; assist the PI to prepare reports and notify the IRB, FDA, and/or safety monitor of all Unanticipated Problems/SAE's.

The research coordinator and co-principal investigators will confirm that all Adverse effects (AE) are correctly entered into the AE log by the coordinator; be available to answer any questions that the coordinators may have concerning AEs; notify the IRB and FDA of all Unanticipated Problems/SAEs and AEs as appropriate. All assessments of AEs will be made by a licensed medical professional who is an investigator on the research.

The research coordinator will confirm that the AEs are correctly entered into the AE log. The Study Monitor will confirm that the adverse events are consistent with the source documents and are reported to the appropriate regulatory bodies, as required.

11.1.5 Monitoring Activities

A safety monitor who is not a study investigator (see section 9.9.1) will conduct safety monitoring after treatment is complete for subjects 1, 5, 10, and 21. Adverse events will be documented and reported as described above.

The following issues will be addressed quarterly or more frequently as necessary:

- Verify receipt of all documents and supplies needed to conduct study
- Informed consent obtained for each participant
- CRF completion
- Investigational product accountability
- Check and review of the regulatory binder and all essential documents
- Clinical supply inventory
- SAE reporting
- Enrollment issues and targets
- Protocol amendment and their approval by the IRB
- Significant protocol deviations
- Personnel changes
- Updated regulatory documentation
- Any other issue as deemed important to the conduct of the study

11.1.6 Study Closure

Upon study closure a final evaluation of the data will ensure that all forms are present and complete. Data will be maintained in a secure location for

the appropriate duration as described in section 10.5. At the conclusion of this term, all forms will be shredded and destroyed. All subjects will be contacted via phone to thank them for their participation and to discuss the study findings as well possible additional treatment options.

11.2 Auditing and Inspecting

The investigator will permit study-related monitoring, audits, and inspections by the Research Quality Assurance Office, IRB, the sponsor, and government regulatory bodies, of all study related documents (e.g. source documents, regulatory documents, data collection instruments, study data etc.). The investigator will ensure the capability for inspections of applicable study-related facilities (e.g. pharmacy, diagnostic laboratory, etc.).

12 Ethics

This study will be conducted in compliance with the protocol approved by the Institutional Review Board, the relevant federal regulations, and IRB policies and procedures and according to Good Clinical Practice standards. No deviation from the protocol will be implemented without the prior review and approval of the IRB except where it may be necessary to eliminate an immediate hazard to a research subject. In such case, the deviation will be reported to the IRB according to its policies and procedures.

All subjects for this study will be provided a consent form describing this study and providing sufficient information for subjects to make an informed decision about their participation in this study. This consent form will be submitted with the protocol for review and approval by the IRB for the study. The formal consent of all subjects will be sought using the IRB-approved consent form. Before a subject undergoes any study procedure, an informed consent discussion will be conducted and written informed consent obtained with a consent form signed by the subject or legally acceptable surrogate if applicable. An investigator-designated research professional will obtain written informed consent from subjects. All subjects will be given a signed copy of the informed consent form.

13 Study Finances

13.1 Funding Source

The study is funded by a grant from Medtronic Sofamor Danek USA, Inc.

13.2 Conflict of Interest

Any investigator who has a conflict of interest (COI) with this study as defined by the policies of the UNC IRB will have the conflict reviewed by a properly constituted Conflict of Interest Review Committee with a committee-sanctioned conflict management plan that has been reviewed and approved by the IRB prior to participation in this study. All investigators will follow the UNC conflict of interest policy.

